7.2 Temporary Discontinuation of Study Intervention

Brief temporary discontinuation of study intervention is permitted during the study, providing inhalation of study intervention is completed within 20 minutes.

Study intervention should be temporarily discontinued in the following circumstance:

1. Clinical intolerance to nebulization.

An individual administration of study treatment will be stopped, and supplemental oxygen resumed, if threshold limits of SpO₂ 89% or heart rate 120 beats/min (or as indicated by the Investigator) are exceeded (see Sections 4.2 and 8.1.2).

The participant may continue with subsequent doses if the Investigator judges that the benefit / risk ratio remains positive. In this case, the instruction to continue should be duly recorded in the participant's hospital file and the subsequent nebulization should be closely monitored.

Refer to Section 6.1 for information on staggered dosing in the first 10 participants.

7.3 Participant Discontinuation/Withdrawal from the Study

A participant may withdraw from the study at any time at his/her own request or may be withdrawn at any time at the discretion of the Investigator for safety, behavioral, or

administrative reasons. The participant will be definitively discontinued from both the study intervention and from the study at that time.

If the participant withdraws consent for disclosure of future information, the Sponsor may retain and continue to use any data collected before such a withdrawal of consent.

If a participant withdraws from the study, he/she may request destruction of any samples taken and not tested, and the Investigator must document this in the site study records.

At the time of discontinuing from the study, if possible, an early discontinuation assessment should be conducted, as shown in the SoA (Table 1-1).

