AE/SAE review	X	X	X	X	X	X	X	
Concomitant medication review	X	X	X	X	X	X	X	
Oxygen / respiratory assessment ⁷	X	X	X	X				
SpO ₂ on room air (after at least 1 minute) prior to study intervention administration and immediately at the end of nebulization ⁶		X	X	X				See Section 8.1.2
Modified WHO ordinal scale	X	X	X	X		X	X	See Section 8.1.1

Procedure	Screening (up to 48 hours before Day 1 ¹)	Intervention Period			Early withdrawal	Efficacy follow-up (Day 14) ² (± 2 days)	EoS efficacy and safety follow-up (Day 28) ² (± 2 days)	Notes
		Day 1 ¹	Daily while hospitalized	Day 10 / hospital discharge				
NEWS 2 assessment ⁷		X	X	X				Prior to study intervention in the morning. See Section 8.1.3

Abbreviations: AE=adverse event; aPTT= activated partial thromboplastin time; CBC=complete blood count; Chem 7=blood chemistry panel (sodium, potassium, chloride, bicarbonate/CO₂, blood urea nitrogen, creatinine, glucose); CV=cardiovascular; ECG=electrocardiogram; LFTs=liver function tests; mHb=methemoglobin; PT/INR=prothrombin time/international normalized ratio; RT-PCR=reverse transcription-polymerase chain reaction; SAE=serious adverse event; TID=three times daily.

1. Screening and randomization may be on the same day, providing all eligibility criteria are met.
2. For participants who are already discharged at either the Day 14 or Day 28 (EoS) follow-up, there will be a phone call to check AEs/SAEs, concomitant medications, and modified WHO ordinal scale. At EoS, safety laboratory tests (nitrite and mHb only) and weight will be collected for participants in hospital only.
3. COVID-19 infection must be confirmed and documented in chart with a positive result on a validated test.
4. At Screening: CBC, chem 7, mHb, LFTs, coagulation (PT/INR, aPTT).
On Day 1, Day 3, Day 7 and Day 10, or early withdrawal: CBC and chem 7 (per SOC).
On Day 28: nitrite and mHb (participants in hospital at EoS only).
5. Vital signs: temperature, heart rate, blood pressure, respiratory rate. Vital signs to be repeated as per SOC during treatment period.
6. Study intervention comprises the following procedures which are to be done in order and as quickly as possible:
 - a. Recording of oxygen flow level including mode (nasal cannula, mask)
 - b. Recording of SpO₂ and heart rate
 - c. Discontinuation of supplemental oxygen administration *
 - d. Close participant oversight by trained health care professional until SpO₂ is stable on ambient air after one minute at least *

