- Experiences an event that requires permanent discontinuation as described in Section 7.1.

In the above cases, participants will be considered as ongoing in the study until the final Safety follow-up phone call (Day 28). Participants will be withdrawn from the study prior to Day 10 (Early withdrawal) only if they withdraw consent.

The total study duration for a participant from screening to last follow up will be up to 30 days (±2 days).

Participants will be stratified by country and presence of risk factor(s) for severe outcomes of COVID-19, based on comorbidities and age, as detailed in Section 6.3.

Two interim analyses are planned (see Section 9.5 for details).

An IDMC will be responsible for closely reviewing the safety and efficacy data from the interim analyses and for providing their recommendations on continuation of the study. The IDMC will meet after 10, 20, 60 and 150 participants have completed the study (see Sections 9.5 and 9.6).

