6.3 Measures to Minimize Bias: Randomization and Blinding

This is an open-label study; however, the specific intervention to be taken by a participant will be assigned using an interactive voice response system (IVRS)/interactive web response system (IWRS). The site will contact the IVRS/IWRS prior to the start of study intervention

administration for each participant. The site will record the intervention assignment on the applicable case report form (CRF), if required.

Potential bias will be reduced using a central stratified randomization to assign participants into one of the study treatment arms, RESP301+SOC or SOC (control), with a randomization ratio of 2:1. Participants will be stratified by country and presence of risk factors for severe outcomes of COVID-19, based on comorbidities and age as follows:

1. Age >65 years
2. Ongoing or currently treated diabetes mellitus
3. Ongoing or currently treated hypertension
4. Ongoing or currently treated cardiovascular disease
5. Ongoing or currently treated chronic lung disease
6. Cancer history of less than 3 years, basal cell skin carcinoma excluded
7. Ongoing or currently treated chronic kidney disease

Participants will be stratified as no risk factor (none of the above criteria), one risk factor (one single of the above) or high-risk factor (2 or more of the above).

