7.1 Permanent Discontinuation of Study Intervention

It may be necessary for a participant to permanently discontinue (definitive discontinuation) study intervention. If study intervention is definitively discontinued, the participant will remain in the study to be evaluated for the Day 14 and Day 28 safety follow-ups. See the SoA (Table 1-1) for data to be collected at the time of discontinuation of study intervention and follow-up and for any further evaluations that need to be completed.

Study intervention will be permanently discontinued prior to 10 days if the participant:

- Improves to level 1 or 2 of the modified WHO ordinal scale;
- Progresses to a level > 4 of the modified WHO ordinal scale.

Additionally, study intervention should be permanently discontinued in the following circumstances:

1. Discontinuation of study intervention for abnormal liver tests should be considered if the Investigator believes that it is in best interest of the participant.
2. If, as part of normal clinical follow-up, a clinically significant change in ECG is identified, the Investigators should exercise their clinical judgement to decide whether continuing study intervention administration is in the best interest of safety of the participant.
3. AE/SAE if the Investigator believes that it is in best interest of the participant, including the following:
 - Development of significant bronchospasm * or worsening of cough that is not tolerated by the participant and leads to immediate discontinuation of the nebulization.
 - Progressive COVID-19 requiring initiation of non-invasive or invasive ventilation or high flow oxygen.
 - Development of mHb level above 3%.
 - Inability to safely continue receiving study intervention due to compromised respiratory status while off supplemental oxygen and receiving nebulized therapy (manifest by drop in SpO₂, increased respiratory rate or clinical other findings).

Refer to the SoA (Table 1-1) for data to be collected at the time of study intervention discontinuation and follow-up and for any further evaluations that need to be completed.

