9.3 Populations for Analyses

For purposes of analysis, the following analysis sets are defined:

Table 9-1 **Populations for Analysis**

Population (Analysis Set)	Description
Intent-To-Treat (ITT) Population	The ITT Population will include all randomized participants. The ITT participants will be analyzed according to randomized treatment, irrespective of the actual treatment received. Participants who withdraw from treatment early will be followed for the assessment of the Day 14 primary endpoint. All efficacy analyses will be performed using the ITT Population.
Per Protocol (PP) Population	The PP Population will include all participants in the ITT Population with no major protocol deviations that may significantly impact data integrity or patient safety. The PP Population will be used for supportive analyses of the efficacy measurements.
Safety Population (SP)	The SP will include all randomized participants who inhale any amount of study intervention or are randomized to the control arm. The SP will be analyzed according to the actual treatment received. This set will be used for the safety analyses.

The ITT Population will be the primary analysis set for all efficacy analyses and the PP Population will be used to demonstrate robustness of results for the primary efficacy endpoint.

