10.5 Appendix 5: Statistical Design Considerations

10.5.1 Some General Design Considerations

1. Binary primary endpoint: progression to critical stage/death up to Day 14
 - to be analyzed by a Cochran-Mantel-Haenszel (CMH) stratified for the factors used in the stratified randomization
 - subjects who withdraw from study treatment will be followed up until their primary endpoint outcome is known (i.e., up to Day 14 or progression to critical stage/death, whatever is first)
 - it is, therefore, not clear what current protocol synopsis text could mean: *If subjects are discharged from the hospital prior to day 14 due to improvement of the clinical status and their status on day 14 cannot be obtained, their status on day 14 for the primary endpoint will be imputed with the status on the day of discharge. and what the implications on statistical study characteristics could be. Further discussion is needed.*
2. Timing of the two planned interim analyses with stopping options is stated as

There are 2 interim analyses planned, the first interim analysis after the first 60 participants have completed day 10 of the observation period ... and a second interim analysis after 150 participants have completed day 14 of the observation period.

With the current text for the timing of the first interim analysis, it is not clear how many subjects will have been randomized at least 14 days prior to the interim data cut-off date and can therefore provide data for the binary primary endpoint (“progression to critical stage/death up to Day 14”).

For such a binary endpoint, Parexel does not recommend including any participant randomized less than 14 days prior to the interim data cut-off date (note this would be different to a study with a time-to-event endpoint) as

- for such participants not yet progressed, the outcome up to Day 14 is unknown and should not be imputed as “not progressed up to Day 14”
- for such participants progressed prior to Day 14, the outcome is known but their inclusion would bias the estimation of progression probability up to Day 14 in a upwards direction.

In order to set up the adaptive group-sequential study design, the following assumptions have been used:

- first interim analysis: a total of ≈ 39 participants randomized at least 14 days prior to data cut-off date
- second interim analysis: a total of $\approx 50\%$ of the initially planned number of participants randomized at least 14 days prior to data cut-off date.

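### Section 7.3 lets the investigator end a participant's whole study participation, against Section 4.1, which leaves an open-label route by which Day 14 outcomes could be lost selectively

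*Protocol*

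**What the plan says.** Section 7.3 of the Protocol, on leaving the study, says that besides leaving at their own request a participant "may be withdrawn at any time at the discretion of the Investigator for safety, behavioral, or" administrative reasons. The consequence is stated without exception: "The participant will be definitively discontinued from both the study intervention and from the study at that time". An early discontinuation assessment follows only if it is possible.

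Four other places take a different line:

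- Section 4.1: "Participants will be withdrawn from the study prior to Day 10 (Early withdrawal) only if they withdraw consent". Participants whose treatment is stopped count as ongoing in the study until the Day 28 contact.
- Section 7.1: "If study intervention is definitively discontinued, the participant will remain in the study", to be evaluated at Day 14 and Day 28.
- Section 9.3, Table 9-1 (ITT Population): "Participants who withdraw from treatment early will be followed for the assessment of the Day 14 primary endpoint".
- Appendix 5, Section 10.5.1: "subjects who withdraw from study treatment will be followed up until their primary endpoint outcome is known".

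Section 6.3 confirms that there is no blinding: "This is an open-label study; however". In the Schedule of Activities (Section 1.3), the row "Modified WHO ordinal scale" is marked at screening, on Day 1, daily in hospital, at Day 10 or discharge, on Day 14 and on Day 28. It is blank under Early withdrawal.

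These texts are from Version 2.0. Version 3.0 is available only in part. Its contents list keeps Section 7.3, and its change table lists no change to 7.3, to the withdrawal rule in 4.1 or to the ITT definition.

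**The concern.** A site that wants to stop RESP301 for a safety reason has two routes. Under 7.1 it stops treatment and keeps the patient under observation. Under 7.3 it may remove the patient from the study, also for safety, and nothing after that moment is collected. No text says which section governs, and before Day 10 the second route is one that 4.1 rules out.

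The decision rests with an investigator who knows the arm. Safety reasons tied to nebulization can arise only on RESP301, and one of the stopping reasons listed in 7.1 is compromised respiratory status, which plausibly goes with a higher risk of progression. If such patients left the study before progressing, the primary comparison would lack some RESP301 events with no matching loss on control. No later analysis can recover an outcome that the site was told to stop collecting.

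**Working it through.** **Step 1. The passages side by side.**

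| Place | Who may end study participation, and when | What happens after a treatment stop |
|---|---|---|
| 7.3 | Participant or investigator, at any time | Investigator withdrawal ends treatment and study together |
| 4.1 | Before Day 10, withdrawn consent only | Stays in the study to Day 28 |
| 7.1 | Not addressed | Stays in the study for Day 14 and Day 28 |
| 9.3 (ITT) | Not addressed | Followed to the Day 14 endpoint |
| Appendix 5 | Not addressed | Followed until the primary outcome is known |

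The contradiction between 7.3 and 4.1 is direct for the period before Day 10. The other three concern withdrawal from treatment. Section 7.3 does not negate them in words, but it defeats the follow-up they promise whenever a site uses it.

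**Step 2. The plan's own figure.** Inputs from Section 9.2: 30% versus 15%, 100 versus 200 participants, one-sided alpha 0.025. With unpooled variance:

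SE = √(0.30×0.70/100 + 0.15×0.85/200) = √(0.0021 + 0.0006375) = 0.0523

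Power = Φ(0.15/0.0523 − 1.960) = Φ(2.867 − 1.960) = Φ(0.907) = 81.8%

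Pooled variance gives 84.9%. At the final-analysis alpha of 0.0249 (Section 9.5), a continuity correction gives 81.2% and Fisher's exact test 81.4%. The stated figure of about 80% is reproduced. No dropout allowance is stated.

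**Step 3. Loss unrelated to outcome.** Power (pooled, alpha 0.0249) is 83.1%, 81.1% and 79.0% at 5%, 10% and 15% loss. That costs little.

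**Step 4. Loss related to outcome.** The documents give no withdrawal rate, so the following are assumptions: no true effect, with 30% progression in both arms; w would-be progressors on RESP301 leave before their event; none leave on control. Interim looks and strata are ignored. Let X ~ Bin(100, 0.30) on control and Y ~ Bin(200, 0.30) on RESP301. The observed RESP301 result is (Y−w)/(200−w) if the lost patients are excluded, and (Y−w)/200 if they are scored as non-events. With p̄ the pooled proportion and n the RESP301 denominator,

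Z = (control rate − RESP301 rate) / √(p̄(1−p̄)(1/100 + 1/n))

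and the null is rejected when Z > 1.9617 (one-sided 0.0249). Summing the exact binomial probabilities over the rejection region gives:

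| w | Share of RESP301 arm | Type I error, excluded | Type I error, non-events |
|---|---|---|---|
| 0 | 0% | 2.6% | 2.6% |
| 4 | 2% | 4.7% | 5.9% |
| 10 | 5% | 10.7% | 15.9% |

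The 2.6% at w = 0 exceeds 2.49% only because the counts are discrete. A variant that draws the RESP301 events from a reduced rate, (60−w)/(200−w) or (60−w)/200, gives 4.6% and 5.7% at w = 4, and 10.1% and 15.4% at w = 10.

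**Step 5. One data set.** Take 30/100 on control and 42/200 on RESP301. Pooled p̄ = 72/300 = 0.24, SE = √(0.24×0.76×0.015) = 0.0523, Z = (0.30 − 0.21)/0.0523 = 1.72, one-sided p = 0.043. Remove four of the RESP301 events: 38/196 = 0.194, p̄ = 68/296 = 0.230, SE = 0.0517, Z = 0.106/0.0517 = 2.05, one-sided p = 0.020. Four lost patients change the conclusion.

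**The case against.** The best defence is that the protocol already separates stopping treatment from leaving the study. A reader might infer from 7.3 that every RESP301 patient stopped for safety leaves without a Day 14 outcome. The documents do not support that: safety stops of treatment fall under 7.1, which keeps the patient in the study, as do 4.1 and Appendix 5. Section 7.3 bites only if an investigator goes further and removes the patient from the study.

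A reader might also infer that 7.3 contradicts the ITT definition. It does not. The ITT set still contains all randomized participants, and the follow-up sentence in Table 9-1 concerns withdrawal from treatment.

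Nor do the documents show that outcomes will be lost in the drug's favour. The modified WHO scale is recorded daily in hospital, so a patient who progresses before withdrawal already has the event, and it is kept. The direction of any bias depends on how the SAP, which is not shown, treats withdrawn patients. Scoring them as progressors would run against RESP301. The only imputation rule stated in Section 9.4.1 covers patients discharged because of improvement; leaving the rest to the SAP is not a fault.

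Finally, ten lost patients, all would-be progressors and all on one arm, is an extreme. It is one third of the 30 events expected on RESP301 at the planned 15% (0.15×200), and one sixth of the 60 expected at 30%.

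All of this stands and limits the point. It does not remove the clash between 7.3 and 4.1 or the blank entry in the Early withdrawal column.

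**Conclusion.** The point holds as an inconsistency with a possible consequence for the primary analysis. Before Day 10, Sections 7.3 and 4.1 give incompatible rules on who may end study participation. Section 7.3 also opens an exception to the Day 14 follow-up promised elsewhere, usable by an investigator who knows the arm. What can be lost is progression after withdrawal, not events already recorded.

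The inflation of type I error calculated above is conditional on purely one-sided, outcome-related loss; it illustrates sensitivity and does not predict what the trial will see. Even the smaller case shown, 2% of the RESP301 arm, brings the error close to or above twice its nominal level. The text should be corrected, although selective loss is a risk that it permits and not one that has been shown to occur. The conclusion also assumes that Version 3.0 kept the wording of 7.3, as its change table suggests.

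**What to change.** Reconcile 7.3 with 4.1 and 7.1 so that an investigator's decision to discontinue a participant ends study treatment only. Study participation should end only on withdrawal of consent, or on loss to follow-up as Section 7.4 already defines it; without that second ground the new text would conflict with 7.4. For everyone else, keep the Day 14 and Day 28 contacts and record the modified WHO level and vital status. Add the modified WHO scale to the Early withdrawal column of the Schedule of Activities, so that those who do withdraw consent have a last status at exit where they agree to the assessment.

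The criteria for stopping treatment in 7.1 need no change for this purpose. The cost is minor edits to a few sections, one added mark in the schedule and a few more follow-up contacts. Those contacts are already planned, by telephone for discharged participants. Sample size and power are unaffected.

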9.4.1 General Considerations

All statistical analyses will be conducted using SAS, Version 9.4 or later. Baseline characteristics will be summarized by treatment arm. For continuous measures the mean and standard deviation (SD) will be summarized. Categorical variables will be described by the proportion in each category. In addition, 95% confidence intervals (CIs) will be computed as indicated.

All the categorical variables including the primary endpoint will be summarized by treatment with the numbers and percentages of the participants. Treatment difference will be tested using a Cochran–Mantel–Haenszel test stratified by 1) country and 2) participant's clinical status at Baseline. For the categorical endpoints, relative risk and its 95% CI will be presented.

All of the continuous variables, including the changes from Baseline, will be summarized by treatment with the means, SD, medians and the ranges. The mixed model with repeated

measurements /analysis of covariance model with treatment, country, participant's clinical status at Baseline and visit as the model term, and Baseline value as the covariate will be used to test for the significance of the treatment difference. Least square means, standard errors, 95% CIs and p-values will be presented.

Time to event endpoints will be analyzed using the Cox Proportional Hazard model with treatment, participant's clinical status at Baseline and country as the model term. The hazard ratio of RESP301+SOC versus SOC will be presented along with 95% CI and p-value from the model. The Kaplan-Meier curves of the time to events will be presented by treatment for each applicable endpoint.

Handling of missing data

If participants are discharged from the hospital prior to Day 14 due to improvement of the clinical status and their status on Day 14 cannot be obtained, their status on Day 14 for the primary endpoint will be imputed with the status on the day of discharge. Depending on the reasons for missing data on the primary endpoint up to Day 14, additional sensitivity analyses will be performed. Further details on handling on missing data will be provided in the SAP.

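### Section 7.3 lets the investigator take a participant off the study for safety, while Section 4.1 keeps the same participant in to Day 28

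*Protocol*

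**What the plan says.** Section 7.3 (Version 2.0) covers leaving the study. Besides leaving at their own request, a participant "may be withdrawn at any time at the discretion of the Investigator for safety, behavioral, or" administrative reasons. The consequence is immediate: "The participant will be definitively discontinued from both the study intervention and from the study at that time". An early discontinuation assessment is to be done if possible.

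Section 4.1 lists the cases in which study treatment stops for good, among them a participant who "Experiences an event that requires permanent discontinuation as described in Section 7.1". In those cases the participant counts as ongoing until the Day 28 call. It adds: "Participants will be withdrawn from the study prior to Day 10 (Early withdrawal) only if they withdraw consent".

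Three other places deal with leaving treatment:
- Section 7.1: after definitive discontinuation, "the participant will remain in the study to be evaluated for the Day 14 and Day 28 safety follow-ups". Its grounds include an AE or SAE at the investigator's judgement.
- Table 9-1 (Section 9.3): "Participants who withdraw from treatment early will be followed for the assessment of the Day 14 primary endpoint".
- Appendix 5 (Section 10.5.1): "subjects who withdraw from study treatment will be followed up until their primary endpoint outcome is known".

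On missing data, Section 9.4.1 gives one imputation rule, which begins "If participants are discharged from the hospital prior to Day 14 due to improvement of the clinical status". It then plans further sensitivity analyses according to the reason for missingness and leaves the detail to the SAP.

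Version 1.0 has the same two conflicting rules, in its Sections 4.1 and 7.2. The Version 3.0 change table lists no specific change to this rule, but Sections 4 and 7 of Version 3.0 are not shown.

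**The concern.** An investigator who takes a participant off RESP301 for safety finds two instructions. Section 4.1 says to keep the participant in the study to Day 28. Section 7.3 allows the investigator to end study participation on the spot. This is a rule about data collection: an SAP can choose how to impute, but it cannot recover a Day 14 status that the site was told to stop collecting.

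The loss need not be balanced. The trial is open-label, and only RESP301 participants can have bronchospasm or intolerance linked to nebulization. If those removed are also more likely to progress, leaving them out makes the RESP301 progression rate look lower than it is.

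**Working it through.** **Step 1: do the rules meet on the same participant?**

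| Event | 4.1 | 7.3 |
|---|---|---|
| Investigator stops treatment for an AE/SAE (a 7.1 ground) | Ongoing to Day 28 | May be taken off the study for safety |
| Investigator removes for behavioral or administrative reasons before Day 10 | Not allowed: consent only | Allowed |

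The consent-only sentence in 4.1 could be read as limited to the cases listed just before it. The first row still conflicts, because a 7.1 event is one of those cases. Section 7.1, Table 9-1 and Appendix 5 speak of leaving treatment. They show the intent to follow participants to Day 14, but each could stand beside a separate route for leaving the study.

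**Step 2: what the schedule collects.** The Early withdrawal column (Section 1.3) has no mark for the modified WHO scale. The scale is recorded daily while the participant is in hospital, so status is known up to removal but not from then to Day 14. Footnote 2 already plans a call at Day 14 and Day 28 that records the scale for discharged participants.

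**Step 3: reproduce the plan's power.** Inputs from Section 9.2: 200 versus 100 participants, 15% versus 30%, one-sided alpha 0.025. With unpooled variance, SE = √(0.30×0.70/100 + 0.15×0.85/200) = √0.0027375 = 0.0523, and power = Φ(0.15/0.0523 − 1.960) = 81.8%. With a continuity correction it is 81.3%. Both agree with the stated figure of about 80%.

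**Step 4: illustrate the possible size.** The test is a pooled z test, an unstratified stand-in for the planned CMH test, at the final one-sided alpha of 0.0249 (Section 9.5). It is evaluated by exact binomial enumeration, with no interim analysis and no sample size increase. With no loss, type I error at 30% in both arms is 2.6% and power at 15% versus 30% is 85%.

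Assumptions, none of them from the protocol: a fraction *w* of the RESP301 arm is removed before the outcome is known; their progression risk is *r*; no controls are removed; true progression is 30% in both arms; the analysis is complete-case. Then n = 200(1 − w) and the observed RESP301 rate = (0.30 − w·r)/(1 − w).

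| w | n | r = 60%: observed rate | False benefit | Type I error | r = 30%: type I error |
|---|---|---|---|---|---|
| 1% | 198 | 29.70% | 0.3 points | 2.9% | 2.6% |
| 5% | 190 | 28.42% | 1.6 points | 4.8% | 2.6% |
| 10% | 180 | 26.67% | 3.3 points | 9.0% | 2.6% |

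Example for w = 5%, r = 60%: (0.30 − 0.05×0.60)/0.95 = 0.27/0.95 = 28.42%.

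The result depends on the imbalance between arms. At r = 60%, equal removal in both arms gives 2.6% to 2.7%. If the control arm loses participants at half the RESP301 rate, the error is 3.6% (5% removed from RESP301) or 5.1% (10% removed).

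**The case against.** The strongest defence is that 7.1 and 7.3 cover different events. The treatment-related safety reasons (AE/SAE, bronchospasm, methemoglobin above 3%, respiratory compromise) all have a specific rule in 7.1 that keeps the participant in the study, and 7.3 is a general residual clause. This stands against 7.1, Table 9-1 and Appendix 5. A reader might infer that four places contradict 7.3 and that all of them require follow-up until the primary outcome is known. The text does not support that: three of the four concern leaving treatment, only Appendix 5 refers to the outcome being known, and 7.1 calls its visits safety follow-ups. The defence does not remove the conflict with 4.1, which restricts leaving the study itself.

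A second defence is that 4.1 ties the Early withdrawal label to withdrawn consent, so the blank cell in that column does not show how safety removals are handled. That is fair; the blank cell is a secondary point.

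A third is that 9.4.1 plans sensitivity analyses for other missing outcomes. It does, so the protocol is not silent on them. They would still have to work without the outcomes themselves.

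Finally, 7.3 also covers participants' own requests and behavioral and administrative reasons, which arise in both arms. The protocol does not plan a complete-case analysis for removed participants either. Both points limit what the numbers can show.

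**Conclusion.** Sections 7.3 and 4.1 conflict in Version 2.0, and the same conflict stands in Version 1.0. Whether it remains in the governing Version 3.0 cannot be confirmed, because Sections 4 and 7 of that version are not shown. The consent-only sentence reaches only to Day 10, but the rule that a 7.1 stop stays in the study runs to Day 28.

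The consequence depends on site practice. Where sites follow 4.1, nothing is lost. Where a site applies 7.3, the Day 14 primary outcome is no longer collected, and removals linked to nebulization fall in one arm only.

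The size is unknown. A reader might take the 2.9% to 9.0% range as the trial's type I error. It is not: it rests on assumed removal of 1% to 10%, none in control, a 60% progression risk and a complete-case analysis. With average risk among those removed, or equal loss in both arms, there is essentially no inflation. This is a wording conflict worth correcting, of low severity, and not evidence that the primary analysis is biased.

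**What to change.** 1. Reword 7.3: for safety, behavioral or administrative reasons the investigator may permanently stop study intervention, but the participant stays in the study, and the modified WHO level is obtained at Day 14 and Day 28, in hospital or by phone, unless consent is withdrawn.
2. In 4.1, delete the words that limit the consent-only rule to the time before Day 10, so that it runs to Day 28.
3. Mark the modified WHO scale in the Early withdrawal column of the schedule, so that status is recorded when a participant withdraws consent.

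The cost is two edited sentences and one schedule cell. No visit is added, since the Day 14 and Day 28 calls already exist. The sample size of 300 and the stated power do not change.
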